4. ADDITIONAL STUDY CONDITIONS

4.1 IRB Approval

Institutional Review Board (IRB) approval is required for each study site according to local requirements and investigator prior to participation in this clinical study. Subject enrollment may not begin until both the IRB and BIOTRONIK, Inc. have granted approval for the study site. IRB approval is also required throughout the duration of this clinical investigation. If IRB approval is withdrawn, BIOTRONIK, Inc. must be notified by the investigator within 5 working days.

4.2 Subject Consent

Subject participation in this study is voluntary. All subjects must sign an IRB approved Informed Consent Form (ICF) prior to participation in the study. Subject informed consent must be obtained prior to enrollment or any protocol related procedures. Informed consent should be obtained in accordance with the FDA regulations (21CFR, Part 50). The investigator is required to inform BIOTRONIK and the reviewing IRB within 5 days if any subject was not appropriately consented to participate in the study. In order to assist with the consent process, BIOTRONIK will provide a template patient consent form to investigational sites participating in the study.

4.3 Data Collection

4.3.1 Electronic Data Capture (EDC)

MedNet Solutions Incorporated is a privately-held company that specializes in web-based clinical data management technology. MedNet will host the EDC system and provide a secure environment that is accessible to authorized individuals through the internet. BIOTRONIK, Inc. will implement a study specific configuration using this software to meet the data collection requirements of the protocol. It is the platform for electronic case report form (eCRF) data entry, query management, and access to clinical data for parties authorized by BIOTRONIK, Inc.

4.3.2 Electronic Case Report Forms (eCRFs)

Original data will be collected from each investigational site and recorded into the EDC system via completion of eCRFs. The investigator will be required to use an electronic signature to approve the content of the data reported in the eCRFs. BIOTRONIK, Inc. will audit and monitor the content of the eCRFs as described in Section 9.

Information from electronically delivered source data (e.g. programmers) will be captured and stored in a validated environment until the end of the study.

4.3.3 BIOTRONIK Home Monitoring® Data

In the QP ExCELS study, data of the study subjects will be accessible to the sponsor via transfer from the Home Monitoring Service Center during the course of study participation of the respective subject. BIOTRONIK Home Monitoring® data might be used for evaluation and publication if desired by the sponsor.

All data are transferred to the sponsor in a pseudonymized form. Data includes all information transmitted from the device (e.g. IEGMs, statistics, lead information).

4.4 Confidentiality of Subject Data

Information sent to BIOTRONIK, Inc. pertaining to study subjects will be kept confidential at BIOTRONIK, Inc. and is subject to audit by IRB and other regulatory authorities. For reporting purposes, data collected from U.S. sites will be shared with BIOTRONIK SE & Co. KG. Information shared with BIOTRONIK SE & Co. KG will be kept confidential. Reports submitted to physicians and data presented in publications of study results will not make any reference to subject name.

In order to verify the study data and ensure study integrity, monitors from BIOTRONIK, Inc., authorized personnel from BIOTRONIK SE & Co. KG, regulatory authorities, and the reviewing IRB may review and/or copy the study records.

4.5 Data Quality Control

BIOTRONIK, Inc. will regularly review study data. At any time, reports can be generated on entered or missing data by BIOTRONIK, Inc. or by approved research personnel at each investigational site. The EDC system will be used to track received and expected visit data and eCRFs for each subject. This system also provides the capability to monitor the status, volume, and disposition of data. In addition, all study data will undergo extensive automatic edit and plausibility checks that provide information to the investigational sites to help improve and maintain data quality control procedures designed to detect inaccuracies and inconsistencies.

4.6 Deviations from Clinical Investigation Plan

The investigator is required to conduct this study in accordance with the signed investigator agreement and clinical protocol. The investigator shall notify BIOTRONIK, Inc. and reviewing IRB in writing no later than 5 working days after any significant deviation from the clinical protocol that has occurred to protect the life or physical well-being of a subject in an emergency. Except in such emergency situations, prior approval by BIOTRONIK, Inc. is required for significant deviations from the clinical protocol.

BIOTRONIK, Inc. categorizes protocol non-compliance instances as either protocol violations or protocol deviations. Both protocol violations and deviations will be reported in the interim and final clinical progress reports.

4.6.1 Protocol Violations

Protocol violations are defined as instances where the protocol requirements and/or regulatory guidelines were not followed, and are generally more serious in nature. Protocol violations are considered to potentially affect the scientific soundness of the study and/or the rights, safety, or welfare of subjects. Protocol violations include, but are not limited to, failure to obtain consent, and subject inclusion/exclusion violations.

4.6.2 Protocol Deviations

Protocol deviations are defined as instances where the requirements of the protocol were not followed in such a manner whereby data is unusable or unavailable. Protocol deviations are less serious in nature and may not require IRB notification as long as they do not affect the rights, safety, or welfare of the study subject.

Informed Consent documentation issues are also considered protocol deviations. These include but are not limited to incomplete ICF, missing dates for signature(s), missing initials or illegible information, subject signature date completed by someone other than subject, utilization of an outdated or non-IRB approved ICF, or incomplete associated forms required at time of consent, etc. (this is not an exclusive list).

4.6.3 IRB Reporting of Non-Compliance

The study site must notify the reviewing IRB of all non-compliance issues per the IRB and protocol reporting requirements. At a minimum, all violations and non-compliance issues related to informed consent and informed consent documentation should be reported to the IRB.

In some instances, such as failure to obtain consent, the study site should also seek guidance from the IRB to ensure the subject received appropriate information to consider her or his participation in the study.

The site should provide a copy of the IRB protocol noncompliance notification (as applicable) to BIOTRONIK.

4.7 Subject Retention

BIOTRONIK, Inc. will provide additional tools to the sites in an effort to minimize the number of subjects that are lost to follow-up. This includes an overview of each subject's visit schedule, including the windows for each visit as they become due. The visit schedule reporting allows research personnel to become alerted to and track all study subjects that should be scheduled for upcoming study evaluations.

In addition, BIOTRONIK, Inc. monitors will review subjects, including those that may be lost to follow-up, to ensure protocol and study visit compliance.

4.8 Study Completion

BIOTRONIK, Inc. will notify the U.S. study site upon completion or termination of the clinical investigation or of the investigator's participation. BIOTRONIK, Inc. will provide a Clinical Investigation Report to each investigational site. BIOTRONIK, Inc. will also determine which sites will have an on-site close out visit and provide details on closure activities to all investigators to ensure the investigator understands any applicable regulatory requirements, including those related to record retention.

5. STUDY OVERSIGHT

5.1 Clinical Events Committee

A Clinical Events Committee (CEC) consisting of at least 3 independent Electrophysiologists or Cardiologists (with CRT experience) will be established to review and adjudicate all MPP sub-study related events (Section 5.1). Protocol defined adverse events that are not MPP sub-study related will be included in the clinical report based on site-reported information.

The CEC will be blinded to the investigational site and subject identity, and to minimize bias members will not participate as investigators. The CEC will create a study specific charter defining the adverse event adjudication process, specifically detailing review guidelines along with appropriate response timelines.

The Clinical Events Committee is responsible for:

- Endpoint adjudication of adverse events meeting the criteria above
- Adjudication meetings, as needed, via telephone conference or face-to-face
- Regular reporting of adjudication results to the sponsor

The Clinical Events Committee will be supported by members of the sponsor in pre-selection of device complications from non-device related adverse events (e.g. broken leg, headache, cancer) and in organizational tasks.

5.1.1 Clinical Events Committee – MPP Sub-Study Events

The QP ExCELS Clinical Events Committee (CEC) described in Section 5.1 will adjudicate all adverse events that require additional invasive intervention to resolve which may be related to the MPP feature. These events include any software issues related to MPP programming or any adverse event that occurs while MPP is enabled and that may be attributed to the use of the MPP feature. The CEC will indicate whether the adverse event is related, possibly related, not related, or has an unknown relation to the MPP feature.

In addition, the CEC will adjudicate all deaths reported while participating in the MPP sub-study and classify each death as cardiovascular, vascular, non-cardiovascular/vascular, or unknown.

The CEC will adjudicate all reported protocol-defined hospitalizations while a subject is enrolled in the MPP sub-study. Hospitalization events will be classified as cardiovascular, vascular, non-cardiovascular/vascular, or unknown. Additionally, hospitalizations classified as cardiovascular will be further classified as a HF hospitalization, non-HF hospitalization, or unknown. Hospitalization events reported by the investigator as part of the initial responder classification for enrollment into the MPP sub-study will not be adjudicated by the CEC.

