2.6 Data Analyses

Descriptive statistics will be used to present and summarize the data collected in the clinical study. Frequency distributions and cross tabulations will be presented for discrete variables. Means, standard errors, and ranges will be presented for continuous variables.

Classification of "HF hospitalization" and "cardiovascular death" events for use in primary endpoint 1, secondary endpoint 2, and secondary endpoint 3 analyses will be determined by a Clinical Events Committee (Section 5.1.1.).

For primary endpoint 1, the lower, one-sided, exact 97.5% bound for the observed proportion of responders ("improved") would have to exceed 3% for rejection of the null hypothesis. Additionally, descriptive statistics will be provided for observed

changes in NYHA class and frequency tabulations provided for the other components of the Clinical Composite Score.

The AE-free rate calculated for secondary endpoint 1 will be based on the total number of subjects with at least one MPP related adverse event requiring additional invasive intervention to resolve. For the secondary endpoint analysis, the AE classification, category, resolution, and relation to the MPP feature for each individual event will be determined by the Clinical Events Committee (CEC) (Section 5.1.1). All adverse events which the CEC determines the event is related or possibly related to the MPP feature will be included in the secondary endpoint 1 analysis. Adverse events with a final CEC adjudicated relation of not related or unknown will not contribute to or be included in the evaluation of the secondary endpoint.

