6.2 Reporting Adverse Events

The investigator has to record any reportable adverse event which occurs during study duration. The adverse event will be classified according to the seriousness, the relation to the implanted devices, and to the procedure. The investigator shall

report to the sponsor, by completing the appropriate eCRF, the following types of events:

- all adverse events related to or possibly related to the implanted system
- any major adverse events related to procedures involved with implanting, using, or testing the implanted system (examples are provided in Section 6.3.1 and definitions are provided in Appendix A: Definition of Terms)
- any adverse device effects, regardless of severity
- any cardiovascular hospitalizations and any other hospitalizations in which cardiovascular symptoms occur during participation in the MPP sub-study (Section 6.3.2 provides definitions)
- most recent heart failure hospitalization that occurs after eligible system implant and before MPP sub-study enrollment (if subject participates in the MPP sub-study; Section 6.1.4 provides definition)
- all adverse events that require additional invasive intervention to resolve, specifically related to the MPP feature of the CRT-D that occur during participation in the MPP sub-study (examples are provided in Section 6.3.3)

Events will be reported on an Adverse Event eCRF. Events should be reported as information is available, even if this results in an incomplete eCRF. The investigator must follow-up all ongoing reportable events either as long as the subject participates in the clinical investigation, the clinical investigation is terminated, or until the event has been resolved, whatever comes first.

The investigator must characterize each event by a single primary diagnosis. The primary diagnosis may describe an event consisting of several clinically recognizable features, symptoms or secondary diagnoses. Note: The observed symptoms and secondary diagnoses must be properly documented in the respective eCRF.

Multiple events may occur simultaneously in one subject. For each medically independent event with a primary diagnosis an individual report must be provided.

In addition, the action taken/treatment should also be provided with any supportive documentation available.

The investigator has to ensure that all relevant information is available. This also includes information from other parties (family, other hospitals, etc.).

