6.3.2 Reporting Hospitalizations

To eliminate possible bias at the site level related to possible endpoint events of the MPP sub-study, adverse events requiring hospitalization for any cardiovascular hospitalizations and any other hospitalizations in which cardiovascular symptoms occur will be collected while subjects are enrolled in the MPP sub-study. Each hospitalization will be adjudicated to determine whether it meets the MPP sub-study endpoint criteria as a heart failure hospitalization by the Clinical Events Committee (CEC).

BIOTRONIK will be responsible for verifying completeness of the initial reported event and coordinating with sites to obtain any missing or additional source documentation required by the CEC to adjudicate the case. Additional documentation will be requested from the enrolling site as needed. The hospital report should include the following, if available:

- Discharge summary
- History and physical and admission summary
- Diagnostic and laboratory test results
- Chest X-ray, echocardiography, ultrasound or other imaging test results, as appropriate
- Consultations, operation reports, progress notes and discharge summaries from the subject medical records
- Investigator description and assessment of the event

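### Secondary Endpoint 1 leaves MPP relation to the CEC, but the CEC is sent only events already thought possibly MPP-related, so the AE-free rate can be right or too high, never too low

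*Combined protocol and SAP*

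**What the plan says.** Section 2.6 gives the endpoint decision to the committee: "relation to the MPP feature for each individual event will be determined by the Clinical Events Committee". Events the CEC rates related or possibly related count; those it rates not related or unknown do not.

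Section 5.1.1 defines what the committee receives. It "will adjudicate all adverse events that require additional invasive intervention to resolve which may be related to the MPP feature", and these events are described as MPP software issues or "any adverse event that occurs while MPP is enabled and that may be attributed to the use of the MPP feature". MPP being on is not enough; attribution is a second condition.

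Section 6.2 lists what sites must report. The MPP item covers "all adverse events that require additional invasive intervention to resolve, specifically related to the MPP feature of the CRT-D", and Section 6.3.3 uses the same trigger. A separate item in 6.2 covers all events related or possibly related to the implanted system.

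Section 5.1 adds two statements. "Protocol defined adverse events that are not MPP sub-study related will be included in the clinical report based on site-reported information". And sponsor staff support the CEC "in pre-selection of device complications from non-device related adverse events", with a broken leg, headache and cancer as examples of the latter. A CEC charter is to be written; it is not part of these documents.

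For hospitalizations, Section 6.3.2 collects every cardiovascular admission, and any other admission with cardiovascular symptoms, for CEC adjudication. It gives the reason: "To eliminate possible bias at the site level related to possible endpoint events of the MPP sub-study".

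**The concern.** Relatedness to MPP is the entire content of this endpoint, yet it is used twice: as the condition for reaching the independent committee and as the question the committee answers. The committee can reject an event it is sent. No section describes how it would find one it was not sent.

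The doubtful cases are easy to foresee. MPP eligibility in Section 3.1.3 depends on LV threshold and absence of phrenic nerve stimulation in at least two vectors, and Section 2.6.2 anticipates lead revisions during the sub-study. Section 6.3.1 lists high threshold, extracardiac stimulation and dislodgement as lead events. An investigator could reasonably log such a revision as a lead event and never raise MPP.

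At stake is the safety estimate from a single-arm post-approval study required by FDA. With no comparator, under-referral would not show up as a difference between arms.

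**Working it through.** **1. The event path, side by side.**

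| Step | Section | Condition on MPP relation |
|---|---|---|
| Site reports an MPP event | 6.2, 6.3.3 | specifically related |
| Site reports a system event | 6.2 | none; relation to the system is enough |
| CEC receives it for MPP relation | 5.1.1 | may be related, or may be attributed |
| Event counts in the endpoint | 2.6 | CEC rates it related or possibly related |

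The MPP reporting trigger is narrower than the counting rule. An event the CEC would call possibly related can fail the first row, enter through the second, and never reach the third. If it also involves a qualifying hospitalization it does go to the CEC, but the task Section 5.1.1 sets there is cardiovascular and heart-failure classification, not MPP relation.

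**2. Direction.** Section 2.6 counts subjects with at least one qualifying event. Let R be the subjects the CEC would count if it rated every invasive-procedure event, and C those actually counted. If the CEC's rating of an event does not depend on how it was referred, C is a subset of R, so

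AE-free rate reported = 1 − |C|/n ≥ 1 − |R|/n.

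Equality holds when nothing is missed.

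**3. The denominator.** The plan gives no expected rate, goal or sample size for this endpoint; its 90 evaluable subjects come from the primary endpoint. That figure reproduces. With an exact binomial, p0 = 0.03, p1 = 0.10 and success at 7 or more of 90, one-sided alpha is 0.0188 and power is 0.8075; at 89, power is 0.798. Enrollment is 90/(1 − 0.10) = 100. Neither number bears on the routing question.

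**4. Size per missed subject.** One subject is worth 1/90 = 1.1 points, 1/100 = 1.0 or 1/110 = 0.9. At n = 90, with exact one-sided 97.5% lower bounds (my choice; none is planned for this endpoint):

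| Subjects counted | AE-free rate | Lower bound |
|---|---|---|
| 0 | 100% | 96.0% |
| 1 | 98.9% | 94.0% |
| 2 | 97.8% | 92.2% |
| 3 | 96.7% | 90.6% |

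**5. Illustration under assumptions.** The documents give neither an MPP event rate nor a referral probability. Suppose n = 100, T subjects have one event each that the CEC would count, and each is referred with probability s. The expected overstatement is T(1 − s)/n. For T = 4, the expected AE-free rate is 96.0% at s = 1, 97.0% at s = 0.75 and 98.0% at s = 0.5. Over T = 2 to 6 and s = 0.5 to 1, the overstatement runs from 0 to 6 × 0.5 = 3 points.

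**The case against.** The strongest reply is that the gap concerns routing only. The Section 5.1.1 threshold is low, the documents do not say who applies it, and the charter may set wider intake. System-related events are captured anyway under Section 6.2, and Section 6.3.1 includes leads repositioned or replaced for any other reason. All of that is fair, and it means the data would exist. It does not close the gap: the protocol text makes attribution a condition of referral, and a protocol-defined endpoint should not depend on an unseen charter to widen it.

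Four stronger readings are tempting, and the documents do not support them.

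- *The sponsor decides which events are MPP-related.* Section 5.1 gives sponsor staff a sort of device from non-device events. A lead revision falls on the device side. No section gives the sponsor attribution to MPP.
- *The Section 5.1 sentence on site-reported information is itself the MPP filter.* It refers to the sub-study, not the feature, and may simply mean events outside the sub-study, since one protocol also covers QP ExCELS subjects who never enter it.
- *The counted events must be too few.* They may equal the correct number if every relevant event is referred.
- *The post-operative rates in Appendix B, Table 9b measure the loss.* They are general device rates, many such events need no invasive procedure, and MPP follow-up starts months after implant. They say nothing about unreferred MPP-related events.

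Nor is this mainly a matter of blinding. The CEC is blinded to site and subject identity only, and every sub-study subject is meant to have MPP on.

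**Conclusion.** The concern stands as a gap in CEC intake. For this endpoint the protocol lacks the attribution-free capture it uses for hospitalizations, and its reporting trigger is narrower than its counting rule. The possible error runs one way: the AE-free rate is unbiased or too high. Its size cannot be derived from the documents; it is about 1.1 points for each subject missed at n = 90, and 0 to 3 points under the illustrative assumptions above.

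A reader might infer a threat to the trial's conclusions. The plan does not support that. Secondary Endpoint 1 has no hypothesis, performance goal or success rule, so no test or type I error is affected. The consequence is a descriptive safety rate that may be optimistic. The conclusion rests on the protocol text alone and would weaken if the charter already requires referral regardless of attribution.

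**What to change.** In Sections 5.1.1, 6.2 and 6.3.3, define intake by what happened rather than by attribution. Send the CEC every reportable adverse event in a fully enrolled subject, from MPP enrollment to exit, that required an additional invasive procedure of any kind, whatever relation the site assigned. Add any other event needing an invasive procedure that the site attributes to MPP. The CEC alone assigns MPP relation, including for events that also reach it as hospitalizations.

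Do not limit intake to generator, lead or pocket procedures: Sections 2.1.2 and 5.1.1 cover any additional invasive intervention, and a narrower list could lose events now included.

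State in Section 5.1 that sponsor pre-selection does not screen these events out. Align the triggers in 5.1.1, 6.2 and 6.3.3 with the related-or-possibly-related counting rule in 2.6, and repeat the intake rule in the charter.

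The cost is a wording change and a few more adjudications among at most 110 subjects, by an existing committee and on events already reported. The AE-free rate may come out slightly less favourable. One limit remains: an event that the site does not report under any item of Section 6.2 would still not be seen.
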